### **8.1.1 Treatment-Emergent Adverse Events**

Summaries of the total number of TEAEs and the number and percentage of subjects with at least one TEAE will be provided. Treatment-emergent AEs will be presented by SOC and PT. At each level of subject summarization, a subject is counted once if the subject reported one or more events. Percentages will be calculated out of the number of subjects in the safety population.

The summary of TEAEs will be presented in alphabetical order of SOC. Within each SOC, PTs will be sorted in descending order from the PT with the highest total to the PT with the lowest total frequency. If the total frequency for any two or more PTs is equal, the PTs will be presented in alphabetical order.

The summarization described above will also be repeated for the following:

- Serious Adverse Events;
- Treatment-Related Adverse Events;
- Treatment-Related Serious Adverse Events;
- Adverse Events Leading to Dose Interruption.

### **8.1.2 Related Adverse Event to Study Treatment**

A summary of related TEAEs to study treatment will be presented in a table. The investigator will provide an assessment of the relationship of the event to the study treatment. Related AEs are those reported as “Possibly Related”, “Probably Related”, or “Related”. If a subject reports multiple occurrences of the same TEAE, only the most closely related occurrence will be presented. Treatment-emergent AEs that are missing a relationship will be considered “Related” and be presented in the summary table but will be presented in the data listing with a missing relationship. Percentages will be calculated based on the number of subjects in the safety population.

The TEAE data will be categorized and presented by SOC and PT in a manner similar to that described in [Section 8.1.1](#).

Related treatment-emergent SAEs to study treatment will also be presented in a table. Treatment-emergent SAEs that are missing a relationship will be presented in the table as “Related” but will be presented in the data listing with a missing relationship.

### **8.1.3 Severity of Adverse Event**

A summary of TEAEs by severity will be presented in a table. The severity that will be presented represents the most extreme severity captured on the CRF page. The possible severities are “Mild”, “Moderate”, and “Severe”.

In the TEAE severity table, if a subject reported multiple occurrences of the same TEAE, only the most severe will be presented. Percentages will be calculated out of the number of subjects in the safety population.

The TEAE data will be categorized and presented by SOC, PT, and severity in a manner similar to that described in [Section 8.1.1](#).

Additionally, the related TEAE data will be categorized and presented by SOC, PT, and severity. If a subject reported multiple occurrences of the same related TEAE, only the most severe will be presented. Percentages will be calculated out of the number of subjects in the safety population.

Treatment-emergent SAEs by severity will also be presented in a table.

### **8.1.4 Adverse Events Leading to Treatment Discontinuation**

A summary of the TEAEs with an action taken with study treatment of “Drug Withdrawn” will be presented in a manner similar to that described in [Section 8.1.1](#).

Any TEAEs leading to treatment discontinuation will be presented in a listing for all subjects.

### **8.1.5 Death**

All subjects who have an AE with an outcome of “Death Related to Adverse Event” will be presented in a listing.

## **8.2 Clinical Laboratory Evaluations**

Summary tables will be presented for clinical laboratory test results (hematology, blood chemistry, and urinalysis) at collection visits for subjects in the safety population. For all fungal diseases except VVC, samples for clinical laboratory tests will be collected at Screening, every 14 days up to EOT if clinically indicated, at EOT, at the 6-Week FU if clinically indicated, and at unscheduled visits if clinically indicated. If indicated, these may be done more frequently as follow-up to a laboratory abnormality. In addition to the above, CPA subjects will have blood drawn on Day 90 and Day 180 for albumin, platelet count, CRP and plasma viscosity assessment. For VVC subjects, safety labs will be collected at Screening, [REDACTED] and 25-

Day FU (32 days after first dose). Safety labs will be repeated at any unscheduled visit, if applicable.

All relevant clinical laboratory tests in chemistry, hematology, and urinalysis will be classified as Low, Normal, and High according to the normal ranges. This categorical data will be summarized in shift tables comparing the extreme results at each visit with those at the baseline visit. Extreme post-baseline results will also be summarized as described in [Section 8.2.2](#). When there are multiple values within a visit for a particular laboratory variable, the worst value will be taken (worst being the smallest value for criteria below a certain threshold or the largest value for criteria above a certain threshold). If a subject has a value below the threshold and above the threshold, the value furthest from the threshold will be chosen.

In data listings, laboratory values will be compared to normal ranges; out-of-range and clinically significant laboratory values will be identified.

### **8.2.1 Pregnancy**

A urine or serum pregnancy test will be performed by the local laboratory for all female subjects of childbearing potential at Screening and will be repeated at EOT for all female subjects of childbearing potential, except those with VVC. Pregnancy tests may be conducted more often (e.g., on a monthly basis), per local regulations. Any subjects with positive pregnancy test results at any time during the study will be presented in a listing.

### **8.2.2 Events of Clinical Interest**

The frequency and percentage of subjects with the following elevations will be summarized at any post-baseline visit:

- ALT or AST  $> 8 \times$  the upper limit of normal (ULN);
- ALT or AST  $> 5 \times$  ULN if new compared to Baseline;
- ALT or AST  $> 3 \times$  ULN and total bilirubin  $> 2 \times$  ULN if new compared to Baseline;
- ALT or AST  $> 3 \times$  ULN.

If subjects meet the criterion ALT or AST  $> 3 \times$  ULN, the additional summary of the frequency and percentage of subjects with ALT or AST  $> 3 \times$  ULN, confirmed by repeat test, and with the appearance of fatigue, nausea, vomiting, right upper quadrant pain or tenderness, fever, rash, and/or eosinophilia ( $> 5\%$ ) will be provided.

A listing will be provided for the above elevations, including the actual measurement of ALT, AST, and total bilirubin, and their reference high limits.

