1. Subject has an invasive fungal disease with central nervous system involvement unless the subject is planned to receive combination therapy with ibrexafungerp and other antifungal.
2. Subject has an inappropriately controlled fungal disease source (e.g., persistent catheters, devices, identified undrained abscess) that is likely to be the source of the fungal disease.
3. Subject is hemodynamically unstable and/or requiring vasopressor medication for blood pressure support.
4. Subject has abnormal liver test parameters: AST or ALT >10 x ULN and/or total bilirubin >5 x ULN.
Note: Subjects with unconjugated hyperbilirubinemia with a diagnosis of Gilbert's disease **are not excluded.**
5. Subject is unlikely to survive 30 days.

Study Drugs:

Ibrexafungerp citrate drug product for oral administration will be supplied as compressed oral tablets containing 250 mg of ibrexafungerp active ingredient on a free base basis. In addition to the active ingredient, the oral tablet formulation also contains silicified microcrystalline cellulose, crospovidone, mannitol, colloidal silicon dioxide, magnesium stearate (non-bovine), and butylated hydroxyanisole. Ibrexafungerp is packaged in bottles containing 30 tablets.

Ibrexafungerp tablets are to be stored at room temperature: between 15°C and 25°C with allowable limited excursions of up to 30°C.

Randomized Treatment Groups: This is an open-label, non-comparator, single-arm study. All subjects will receive ibrexafungerp monotherapy except subjects with refractory or relapsing invasive pulmonary aspergillosis (IPA), mucormycosis or other molds with unpredictable ibrexafungerp activity, who will receive combination therapy. Combination therapy may also be administered to other subjects based on Investigator's judgement and contingent on Sponsor approval. Subjects will receive ibrexafungerp on an inpatient or outpatient basis, as needed for each fungal disease.

Ibrexafungerp Monotherapy for All fungal Diseases, Excluding VVC

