11.2 Exclusion Criteria

A subject will be excluded from participation in the study if he or she meets any of the following exclusion criteria at Screening and/or Baseline:

1. Subject has an invasive fungal disease with central nervous system involvement unless the subject is planned to receive combination therapy with ibrexafungerp and other antifungal.
2. Subject has an inappropriately controlled fungal disease source (e.g., persistent catheters, devices, identified undrained abscess) that is likely to be the source of the fungal disease.
3. Subject is hemodynamically unstable and/or requiring vasopressor medication for blood pressure support.
4. Subject has abnormal liver test parameters: AST or ALT $>10 \times$ ULN and/or total bilirubin $>5 \times$ ULN.

Note: Subjects with unconjugated hyperbilirubinemia with a diagnosis of Gilbert's disease **are not excluded.**

5. Subject is unlikely to survive 30 days.
6. Subject has any other condition or laboratory abnormality that, in the judgment of the Investigator, would put the subject at unacceptable risk for participation in the study or may interfere with the assessments included in the study.
7. Subject requires treatment with the prohibited medications.
8. Subject has known hypersensitivity to ibrexafungerp.
9. Subject is pregnant or lactating.
10. Subject has received any other investigational drug (i.e., new chemical entity) within at least 30 days (or 5 and a half half-lives of the investigational product) before signing the ICF.
11. Subject is an employee of SCYNEXIS, Inc., the Investigator, or contract research organization involved in the study, or an immediate family member (partner, offspring, parents, siblings, or sibling's offspring) of an employee involved in the study.

12. Subject or legal representative is/are unable to provide written informed consent for any reason.
13. Subject is unlikely to comply with protocol requirements.

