14.3.3 Clinical Laboratory Safety Assessments

Clinical laboratory tests will include hematology, blood chemistry and urinalysis.

For all fungal diseases except VVC, samples for clinical laboratory tests will be collected at Screening, every 14 days up to EOT if clinically indicated, at EOT, at the 6-Week FU if clinically indicated, and at unscheduled visits if clinically indicated. If indicated, these may be done more frequently as follow-up to a laboratory abnormality.

In addition to the above, if still on treatment, CPA subjects will have blood drawn on Day 90 and Day 180 for albumin, platelet count, CRP and plasma viscosity assessment.

For VVC subjects, safety labs will be collected at Screening, [REDACTED] and 25-Day FU (32 days after first dose). Safety labs will be repeated at any unscheduled visit, if applicable.

The following laboratory parameters will be determined:

Hematology

▪ White blood cell (WBC) count ^a	▪ Hemoglobin
▪ Red blood cell (RBC) count	▪ Hematocrit
▪ Platelet count ^b	▪ C-reactive protein ^b
	▪ Plasma viscosity ^b

a: Differential WBC count will include percentages for segmented neutrophils, lymphocytes, monocytes, eosinophils and basophils, and absolute counts for neutrophils, lymphocytes, monocytes, eosinophils and basophils.

b: On Day 90 and Day 180 for CPA subjects only.

Blood Chemistry

▪ Sodium	▪ Glucose
▪ Potassium	▪ Albumin ^a
▪ Alkaline Phosphatase	▪ Aspartate aminotransferase (AST/SGOT)
▪ Chloride	▪ Alanine aminotransferase (ALT/SGPT)
▪ Blood urea nitrogen (BUN)	▪ Gamma glutamyl transferase (GGT)
▪ Creatinine	▪ Lactate dehydrogenase (LDH)
▪ Total creatine phosphokinase (CPK)	▪ Bilirubin (total, direct, and indirect)
▪ Total protein	▪ Prothrombin (PT) and international normalized ratio (INR)

a: On Day 90 and Day 180 for CPA subjects only if still on treatment.

Urinalysis

▪ Appearance (clarity, color)	▪ Glucose
▪ Specific gravity	▪ Ketones
▪ pH	▪ Protein
▪ Blood	▪ Leukocytes
▪ Bilirubin	▪ Urobilinogen

Reflex Microscopic Evaluation

▪ Bacteria	▪ Mucous
▪ Casts	▪ RBC
▪ Crystals	▪ WBC
▪ Epithelial cells	

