16.3 Events of Clinical Interest

The following are considered events of clinical interest (ECIs) if they occur after dosing, and must be reported by the site when it becomes aware of the ECI:

- ALT or AST $>8 \times$ ULN, if new compared to Baseline, confirmed by repeat testing
- ALT or AST $>5 \times$ ULN for more than 2 weeks and if new compared to Baseline, confirmed by repeat testing

- ALT or AST >3 x ULN and total bilirubin >2 x ULN and if new compared to Baseline, confirmed by repeat testing
- ALT or AST >3 x ULN, confirmed by repeat testing, with the appearance of fatigue, nausea, vomiting, right upper quadrant pain or tenderness, fever, rash, and/or eosinophilia (>5%)]

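### The SAP's liver table (8.2.2) is titled Events of Clinical Interest but uses looser criteria than protocol 16.3, so its counts are not the protocol's event counts

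*SAP*

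**What the plan says.** Protocol section 16.3 defines four ECIs, all of them liver findings arising after dosing:

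- ALT or AST >8 x "ULN, if new compared to Baseline, confirmed by repeat testing".
- ALT or AST >5 x "ULN for more than 2 weeks and if new compared to Baseline, confirmed by repeat testing".
- ALT or AST >3 x ULN with total bilirubin >2 x "ULN and if new compared to Baseline, confirmed by repeat testing".
- ALT or AST >3 x ULN, confirmed on repeat, with listed symptoms or eosinophilia. This one carries no condition that the elevation be new.

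SAP section 8.2.2 has the same heading. It says "The frequency and percentage of subjects with the following elevations will be summarized at any post-baseline visit", then lists >8 x ULN with no further condition; >5 x ULN if new; >3 x ULN with bilirubin >2 x ULN if new; and >3 x ULN alone. It adds a separate summary of >3 x ULN confirmed on repeat with the protocol's symptoms. A listing is to give the ALT, AST and bilirubin measurements with their upper limits.

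Protocol section 11.2, exclusion criterion 4 (also in the synopsis), sets the entry limit: "Subject has abnormal liver test parameters: AST or ALT >10 x ULN".

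**The concern.** The SAP keeps some of the protocol's conditions and drops others without giving a reason, and its document history records no change to section 8.2.2. A reader of the study report would take a table titled Events of Clinical Interest to hold the events that the protocol defines under that name. It would not.

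This matters more than usual here. Safety is one of the two primary endpoints and there is no control arm, so the absolute count is what will be read. These liver criteria are the only ECIs in the protocol. High values at entry are also plausible: toxicity of earlier antifungal treatment is a reason for enrolment, and one example in the notes to protocol Table 5 is hepatotoxicity with transaminases above 5 x ULN. Without the condition that the elevation be new, liver injury carried in from earlier treatment can appear in the study drug's ECI table.

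**Working it through.** No figure in the plan is at stake, so the main check is a comparison of the two lists.

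| Protocol 16.3 criterion | Conditions in protocol | Conditions kept in SAP 8.2.2 | Dropped |
|---|---|---|---|
| >8 x ULN | new; repeat | none | new; repeat |
| >5 x ULN | over 2 weeks; new; repeat | new | over 2 weeks; repeat |
| >3 x ULN and bilirubin >2 x ULN | new; repeat | new | repeat |
| >3 x ULN with symptoms | repeat; symptoms | repeat; symptoms | nothing |

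The condition that the elevation be new is missing from one criterion, the duration from one, and repeat confirmation from three of four. The SAP also adds a row, >3 x ULN alone, that is not a protocol ECI. Each altered row is broader than its protocol counterpart, so its count can only equal or exceed the protocol count.

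**Does any other part of the SAP text restore the conditions?**

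- *Shift tables (section 8.2).* Results "will be classified as Low, Normal, and High according to the normal ranges". A subject stable at 9 x ULN and one who rises from 2 x to 9 x ULN both go from High to High.
- *Several values within a visit (section 8.2).* The worst is taken, so a repeat at the same visit that fails to confirm the elevation has no effect.
- *Adverse event summaries (section 8.1).* Protocol section 18.6.2 plans a summary of AEs of special interest; SAP section 8.1 specifies none.
- *Listing in section 8.2.2.* Its text asks for neither the baseline value nor confirmation status.

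**Illustration of size for the >8 x row.** Let p be the share of subjects who enter above 8 x and up to 10 x ULN and stay above 8 x. Assume also that nobody has a new elevation above 8 x. With n = 220 (protocol section 18.1), the SAP row shows about p x 220 subjects and the protocol-defined count is 0 by construction. The documents give no value for p, so a range is used. The Clopper-Pearson 95% limits show scale only; the SAP does not plan intervals for this table.

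| Assumed p | p x 220 | SAP row | 95% CI |
|---|---|---|---|
| 0.5% | 1.1 | 1/220 = 0.5% | 0.01% to 2.5% |
| 2% | 4.4 | 4/220 = 1.8% | 0.5% to 4.6% |
| 5% | 11 | 11/220 = 5.0% | 2.5% to 8.8% |
| Protocol definition, any p | – | 0/220 = 0% | 0% to 1.7% |

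For x = 0 the upper limit is 1 − 0.025^(1/220) = 1.7%.

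The excess in the >5 x row and in the >3 x row with bilirubin depends on how many new elevations have no confirming repeat and, at >5 x, how many last two weeks or less. The documents do not allow an estimate of either.

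**The case against.** The strongest reply is that protocol section 16.3 tells sites what to report and does not prescribe a table. The protocol's safety analysis section does not mention ECIs, and the primary safety endpoint refers to laboratory tests in general. SAP section 8.2 introduces 8.2.2 as a summary of extreme post-baseline results, so it may be meant as a broad threshold screen under a borrowed heading. Such a screen errs on the safe side. It also suits the sampling: for subjects without VVC, safety laboratory tests are taken "every 14 days up to EOT if clinically indicated, at EOT, at the 6-Week FU if clinically indicated", so EOT is the only post-baseline draw not conditional on clinical indication. Confirmation and duration will then sometimes be impossible to establish, and a table limited to confirmed cases could miss real elevations. Finally, the SAP promises individual listings to support the tables, from which baseline and repeat values might be read.

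Much of this stands. The direction is conservative, a threshold screen is worth having, and the extra >3 x row does no harm as a screen. The list of tables and listings is kept outside the SAP, so one can say only that the SAP text specifies no table of protocol-defined ECIs. But none of this justifies calling threshold counts ECIs, and working out events subject by subject from listings does not replace a planned count. Missing repeats are a reason to report unconfirmed cases separately, not to merge them with confirmed ones.

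**Conclusion.** The point holds. As written, SAP section 8.2.2 does not give the protocol's ECI count for three of the four criteria, and nothing else in the SAP text supplies it. The text comparison is certain. The effect is over-inclusion: no protocol ECI is missed, but the table cannot show which cases above 8 x ULN are new, or which cases in the first three rows are confirmed.

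The size is unknown. The range of 1 to 11 subjects out of 220 in the >8 x row rests on assumed shares of 0.5% to 5% and on there being no true event; it shows what could happen and is not an estimate. This should be corrected before the tables are produced. It does not threaten the validity of the study.

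**What to change.** Reconcile SAP section 8.2.2 with protocol section 16.3:

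1. Tabulate the four ECIs with the protocol's own conditions, and state how new, confirmed by repeat and over 2 weeks are derived from the laboratory data.
2. Within each ECI, show confirmed cases and cases with no repeat available on separate lines, so that a new elevation first seen at EOT is not lost.
3. Keep the plain threshold counts, including >3 x ULN alone, under the label laboratory elevations, and show the baseline value in the table or the listing.

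The cost is SAP wording and some extra programming on data already collected. No visit, sample or aspect of patient management changes.

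### SAP 8.2.2 tabulates three of the four liver events of clinical interest under looser criteria than Protocol 16.3, so the table can over-count them

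*SAP*

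**What the plan says.** Protocol 16.3 introduces its list with "The following are considered events of clinical interest (ECIs) if they occur after dosing, and must be reported by the site" and gives four criteria, all on ALT or AST:

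- >8x is qualified as "ULN, if new compared to Baseline, confirmed by repeat testing".
- >5x is qualified as "ULN for more than 2 weeks and if new compared to Baseline, confirmed by repeat testing".
- >3x together with total bilirubin >2x ULN is qualified as "and if new compared to Baseline, confirmed by repeat testing".
- >3x with listed symptoms or eosinophilia must be confirmed by a repeat, with no condition on newness.

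SAP 8.2.2 has the same title and opens with "The frequency and percentage of subjects with the following elevations will be summarized at any post-baseline visit". Its four rows are >8x ULN with no further condition; >5x ULN if new; >3x ULN with bilirubin >2x ULN if new; and >3x ULN with no further condition. For subjects in the last row it adds a summary of elevations "confirmed by repeat test, and with the appearance of fatigue, nausea, vomiting, right upper quadrant pain or tenderness, fever, rash" and eosinophilia. It also states: "A listing will be provided for the above elevations, including the actual measurement of ALT, AST, and total bilirubin".

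On entry, Protocol 5.0 (repeated in 11.2) excludes "AST or ALT >10 x ULN and/or total bilirubin >5 x ULN". A transaminase of 9x ULN, or of exactly 10x, is therefore eligible.

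**The concern.** The two sections share a name but count different things. A reader of the study report will take the SAP table to be the frequency of protocol-defined events. For three of the four criteria it is the frequency of a broader set.

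The missing newness condition in the >8x row is the most awkward, because the protocol admits subjects with markedly raised transaminases and Table 5 (footnote b) gives hepatotoxicity from an earlier antifungal as an example of a qualifying toxicity. That does not mean such subjects still have raised values at Baseline, but some may. One whose values were high before the first dose and did not change would appear in a table of on-study liver events.

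Laboratory tests are part of the primary safety endpoint (Protocol 9.1), so the meaning of the row labels should be exact.

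**Working it through.** No figure in the plan needs reproducing. The check sets the two rule sets side by side and runs simple cases through both.

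**Conditions by criterion**

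| ALT/AST criterion | Protocol 16.3 | SAP 8.2.2 | Missing in SAP |
|---|---|---|---|
| >8x ULN | new; confirmed | threshold only | new; confirmed |
| >5x ULN | more than 2 weeks; new; confirmed | new | duration; confirmed |
| >3x with bilirubin >2x | new; confirmed | new | confirmed |
| >3x with symptoms or eosinophilia | confirmed | confirmed | nothing |

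Nothing elsewhere in the SAP restores the missing conditions, and the version 1.1 change history does not mention 8.2.2. SAP 8.2 takes the worst value when a visit has several. If that rule is applied here, a normal repeat within the same visit does not remove the count.

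**Working definitions (assumed; neither document gives them).** *New* means the row's own criterion was not met at Baseline. *Confirmed* means it was met at two consecutive tests.

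**Cases.** Values are multiples of ULN. Results are in the order >8x; >5x; >3x with bilirubin >2x, where 1 means counted.

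| Course | SAP 8.2.2 | Protocol 16.3 | Reason for the difference |
|---|---|---|---|
| Baseline 9, stays at 9 | 1, 0, 0 | 0, 0, 0 | not new |
| Baseline 10, improves to 8.5 | 1, 0, 0 | 0, 0, 0 | not new |
| Baseline 1, rises to 8.5, repeat 2 | 1, 1, 0 | 0, 0, 0 | not confirmed |
| Baseline 1, at 6 for 3 days, then 2 | 0, 1, 0 | 0, 0, 0 | too short |
| ALT 1 to 4 with bilirubin 2.5 once, repeat normal | 0, 0, 1 | 0, 0, 0 | not confirmed |
| Baseline 9, rises to 20 | 1, 0, 0 | 0, 0, 0 | not new |
| Baseline 1, at 6 for 21 days | 0, 1, 0 | 0, 1, 0 | none |
| ALT 4 with bilirubin 2.5 on two tests | 0, 0, 1 | 0, 0, 1 | none |

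These cases show how the rules behave. They were chosen for that purpose and say nothing about how often each course will occur.

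**Direction.** In each of the three rows the SAP condition is the protocol condition with one or more requirements removed. Anything that satisfies 16.3 therefore satisfies the SAP row, and the SAP count is at least the 16.3 count.

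**Internal consistency.** The first two cases count in the >8x row but not in the >5x row, because only the latter asks for newness. The >8x count could therefore exceed the >5x count in the same table. That suggests a drafting slip more than a deliberate simplification.

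**The case against.** The best defence is that 8.2.2 is a laboratory screen and not an event count. SAP 8.2 introduces it as a summary of extreme post-baseline results, and 8.2.2 calls its rows elevations. Protocol 16.3 is a reporting rule for sites, and Protocol 18.6.2 asks only for observed values, changes from Baseline and reference-range shifts. Interim tests outside VVC are drawn only when clinically indicated, so requiring a repeat could lose real elevations that nobody retested. The study is exploratory, its safety analyses are descriptive, and no test or stopping rule depends on these rows. The listing gives the actual values, so the high-baseline subjects could be picked out by hand.

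Most of this stands, and it is why the point is minor and why the present counts should be kept. It does not remove the mismatch. The section's title presents the rows as the protocol's events, and the symptomatic summary shows that the SAP meant to apply 16.3 at least in part. A listing is not a count under the protocol definition, and the SAP plans none for these three criteria.

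The rise from 9x to 20x also deserves weight. It is true worsening, the SAP row counts it, and literal use of 16.3 would not. Not every extra count is spurious, so the stricter rows should be added beside the present ones and should not replace them.

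**Conclusion.** The mismatch is confirmed for three of the four criteria. It runs one way: the >8x, >5x and joint bilirubin rows include every 16.3 event and can include more. Its size cannot be given, because the documents do not say how many subjects enter above 8x ULN or how many elevations will be transient or unrepeated. The example of a subject stable at 9x rests only on the eligibility ceiling and the SAP wording. The treatment of the other cases rests on the working definitions of *new* and *confirmed*.

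A reader might infer more than this. Three stronger readings are not supported:

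- That the table could hide liver events. It cannot for these criteria, since the SAP rows contain the 16.3 events, and the fourth criterion is implemented.
- That the reported liver event rate will be materially inflated. No document shows that anyone enters above 8x.
- That the laboratory plan as a whole is deficient for subjects with abnormal baselines, including for creatinine or isolated bilirubin. Neither is a 16.3 event, and the reference-range shifts and changes from baseline are what Protocol 18.6.2 asks for.

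Severity is minor: a labelling and definition error in a descriptive safety table.

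**What to change.** In SAP 8.2.2:

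1. Add three rows with the Protocol 16.3 conditions in full: >8x ULN, new and confirmed; >5x ULN for more than 2 weeks, new and confirmed; >3x ULN with bilirubin >2x ULN, new and confirmed.
2. Define *new* as the row's criterion not being met at Baseline, and state how confirmation and duration are derived from the test dates.
3. Keep the present counts as separate rows labelled *any post-baseline elevation*.
4. Show elevations with no later test as *not retested*, apart from those that a repeat failed to confirm.

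The symptomatic >3x summary needs no change.

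The cost is a short SAP revision and some programming on data already collected, with no protocol amendment and no extra testing. The downside is that confirmation, and likewise the two-week duration, can be shown only where a further test was drawn. The any-elevation rows must therefore stay, so that unconfirmed elevations and worsening from an already high baseline remain visible.
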